### **5.0 STUDY PLAN**

#### **5.1 Study Procedures**

Temozolomide will be given as per standard of care. Typical dosing is 150 to 200 mg/m^2 on Days 1 through 5 of a 28-day treatment cycle. Patients will be randomized to take their temozolomide doses in the morning (before 10:00) or evening (after 20:00). Compliance with dosing times will be verified by means of a medication diary (Appendix B). Patients who miss taking their dose at the assigned time will be instructed to take the dose as soon as they can (as long as the next scheduled dose is at least 12 hours away) rather than omitting it.

Patients will be given an ActTrust Condor Instrument watch after signing the consent form. Patients will be required to wear the ActTrust Condor Instrument watch 24 hours per day; it should only be removed at specified data collection time points (see protocol calendar 9.0). Actimetry data will be collected at corresponding time points with the return of the patient to clinic every 8 weeks. The ActTrust watch does not require the patient to charge the device, thus the patient will never have to remove the watch and a new, fully charged, watch will be provided to the patient at every collection time point.

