## **7.2 Wrist Actimetry and Sleep Questionnaire**

The ActTrust Condor Instrument watches are wrist actimetry/accelerometers. Large datasets from these devices can be accessed and analyzed through ActStudio (Condor Instruments). This technology has been used already by several groups at Washington University in St. Louis.

Patients will wear an accelerometer on their wrist to measure activity level during the day and at night until two months after the end of treatment. The accelerometer will appear similar to an athletic wristwatch. Patients will be required to wear the accelerometer at all times starting at the beginning of treatment or as soon as they are enrolled in the study, whichever is later. Patients will remove the accelerometer only during situations when the accelerometer would be completely submersed in water or liquid. Wrist actigraphy will be quantified in one-minute bins for the duration of the recording (typically 60 days per patient). The data (counts per minute) will be quantified in terms of average activity per day, percent of activity during waking, percent of activity during sleep, chronotype (average time of daily mid-sleep), chronotype variability (e.g. cycle-to-cycle standard deviation of daily chronotype), sleep duration, nap duration, and number of naps per day. This data will be collected once every 2 months. Patients will not need to charge the watch and upon data collection, a new watch (that is fully charged) will be available for them to take. Once data are collected, it will be analyzed for sleep/wake cycles and overall activity level. Total activity will be measured as average acceleration over 24 hours. Patterns of acceleration will also be noted relative to treatment times in 2 hour increments.

At baseline and at the beginning of each cycle of TMZ, the patient will complete a sleep questionnaire that will be used in conjunction with the ActTrust watch. This qualitative data (sleep questionnaire) will be used with the quantitative data (collected via the ActTrust watch) to assess the level of disruption in sleep/wake cycles experienced by the patient while on study. This data will be collected up to 1 month after the last TMZ treatment. These sleep questionnaires will be administered during an office visit by the study coordinator.

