## **13.2 Data Analysis**

### **13.2.1 General Considerations**

All data will be evaluated as observed, and no imputation method for missing values will be used. All data will be presented in a descriptive manner. Each cohort will be analyzed separately, and no multiplicity adjustment across cohorts will be

performed. All other analyses are considered as exploratory, even if statistical tests are used.

Descriptive statistics will be used to summarize the trial results, i.e., statistics for continuous variables may include means, medians, ranges and appropriate measures of variability. Qualitative variables will be summarized by counts and percentages. The uncertainty of estimates will be assessed by confidence intervals. Unless otherwise specified, the calculation of proportions will be based on the sample size of the population of interest. Counts of missing observations will be included in the denominator and presented as a separate category if not otherwise specified in the statistical analysis plan (SAP).

Duration of response, according to RANO, will be calculated for each subject and will be analyzed using the Kaplan-Meier method in the primary cohorts separately.

PFS will be presented in subject listings and analyzed using the Kaplan-Meier method in the primary cohorts separately.

Correlation analysis (significance at  $R^2 \geq 0.8$ ) and slope analysis (Fisher's Exact Test) of dependent variables (naps/day, nap duration, sleep duration, % activity during waking, % activity during sleep, chronotype, chronotype variability) and independent variables (tumor grade, time since TMZ administration, time of day of TMZ administration, time since diagnosis date, tumor size, immune health) will be carried out. Each variable will be calculated daily and averaged over the collection period. Daily calculation reveals stability, while the average reveals variability.

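### Section 13.2.1 does not say whether daily values or period means enter the actigraphy correlations; on period means, the within-cycle relation of temozolomide dosing to sleep is lost or strongly attenuated.

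*Combined protocol and SAP*

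**What the plan says.** Section 13.2.1 plans correlation and slope analyses of seven sleep and activity variables against "independent variables (tumor grade, time since TMZ administration, time of day of TMZ administration, time since diagnosis date, tumor size, immune health". The rule for forming the variables, with the reason given for it, is "Each variable will be calculated daily and averaged over the collection period. Daily calculation reveals stability, while the average reveals variability". No unit of analysis, definition of time since TMZ administration, or model for repeated days within a patient follows.

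The collection period appears in two forms. Section 5.1 says "Actimetry data will be collected at corresponding time points with the return of the patient to clinic every 8 weeks". Section 7.2 says once every 2 months, with a recording of typically 60 days per patient.

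Section 5.1 describes typical dosing as "Days 1 through 5 of a 28-day treatment cycle", and section 6.0 leaves dose delays to standard of care. The watch may be worn for up to 2 weeks before the first dose (9.0) and is worn until two months after treatment (7.2).

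Section 7.2 also describes "chronotype variability (e.g. cycle-to-cycle standard deviation of daily chronotype", and says that acceleration patterns will be noted relative to treatment times in 2-hour increments.

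**The concern.** Days since last dose change from day to day within a cycle. Averaging both this predictor and the sleep variable over about two cycles removes that change. What is left in the averaged predictor reflects how the window falls on the schedule, whether a cycle was late, and whether the patient was still on treatment. A correlation on such means could be reported as a dose-timing relation when it mostly compares delayed or off-treatment periods with on-schedule ones.

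The other reading, pooling the daily values, has its own fault. Each patient contributes about 56 correlated days per period, and nothing in 13.2.1 accounts for that.

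Section 2.0 says the study is to supply pilot data for future glioma chronotherapy trials, and section 1.7 lists rest-activity rhythms among its five means of assessment. A diluted or delay-driven estimate could mislead the next trial about whether morning or evening dosing disturbs sleep.

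**Working it through.** The plan gives no effect size, SD or power for this analysis, so there is no figure of its own to reproduce. The check is arithmetic on the schedule.

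**Inputs.** Dosing on 5 of 28 days (5.1, typical). Collection period 56 days (5.1), or about 60 to 61 days (7.2). Assumption: time since TMZ administration means days since last dose, counted as 0 on a dosing day. Delay and carry-over lengths below are also assumptions, because the documents give none.

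**The averaged predictor, on schedule.** Days 1 to 5 score 0 and Days 6 to 28 score 1 to 23.
- One cycle: sum = 23 × 24 / 2 = 276; mean = 276/28 = 9.86 days.
- A 56-day window is exactly two cycles: 552/56 = 9.86, whatever the start day.
- A 60-day window adds four days. If all four are dosing days: 552/60 = 9.2. If they are the last four days of a cycle: (552 + 20 + 21 + 22 + 23)/60 = 638/60 = 10.6.
- Kept daily, the predictor runs from 0 to 23 with SD √(4324/28 − 9.857²) = 7.57, where 4324 is the sum of squares of 1 to 23.

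**The averaged predictor, off schedule or off treatment.**
- First cycle delayed by 7 days, 56 days from Day 1: the 35-day cycle sums to 30 × 31 / 2 = 465 and the next 21 days to 16 × 17 / 2 = 136; (465 + 136)/56 = 10.7.
- Second cycle delayed instead: the extra days fall outside the window, so 9.86 again.
- Every cycle 35 days long: from 601/56 = 10.7 to (465 + 420)/56 = 15.8 by start day, where 420 is the sum of 10 to 30.
- First period with 14 pre-dose days: mean over the 42 on-drug days = (276 + 45)/42 = 7.6.
- A 56-day period with no dosing: 28.5 days if it starts the day after the last dose (1 to 56), and 51.5 if it starts after a completed 28-day cycle (24 to 79).

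Most of the spread therefore comes from delays and treatment end, not from closeness to a dose.

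**Dilution of an effect confined to dosing days** (window length ÷ dosing days in it).
- 56 days: 56/10 = 5.6. As an illustration, a 60-minute sleep loss on dosing days shifts the period mean by 60 × 10/56 = 10.7 minutes.
- 60 days: 60/14 = 4.3 to 60/10 = 6.0.
- 61 days: 61/15 = 4.1 to 61/10 = 6.1.
- Carry-over of 2, 5 or 9 days beyond dosing, on 28-day cycles: 28/7 = 4.0, 28/10 = 2.8, 28/14 = 2.0.

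**The wording.** A mean carries no information on variability, so the stated reason for averaging is wrong. Section 7.2 makes chronotype variability a standard deviation of daily values. It needs several days, so the instruction to calculate each variable daily cannot apply to it.

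**The case against.** A reader might infer that averaging makes the predictor a constant, that every dosing-day effect shrinks 5.6-fold, and that the dose-to-sleep relation cannot be derived at all. The documents do not support these stronger readings.

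- Daily values are calculated too, and 13.2.1 gives them a use. The text leaves the choice of form open; it does not discard the daily values.
- The averaged predictor is constant only for on-schedule, on-treatment 56-day windows. The 60-day recording, permitted delays, and wear before and after treatment all break exact constancy.
- The 5.6 figure needs a 56-day window and no carry-over.
- The relation can be derived from data already collected: one-minute bins (7.2) and diary dosing times (5.1).
- Time since TMZ administration is undefined. Read as time since TMZ start, parallel to time since diagnosis in the same list, 56-day period means would be 27.5, 83.5 and 139.5 days, and the constancy argument would not apply.
- The stated aim (2.2 item 5; 13.1.2 item 5) is to relate sleep patterns to outcome by arm. That is a between-patient question, and period means can serve it.
- Section 13.2.1 makes presentation descriptive and calls its other analyses exploratory.

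All of this stands and limits the point. It does not remove it. Section 13.2.1 assigns the daily values only to showing stability and gives no patient term for them, so neither form yields a sound dose-to-sleep result as written. The 2-hour alignment in 7.2 concerns acceleration, not the seven variables listed in 13.2.1, and the statistical section does not take it up.

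**Conclusion.** The point holds as a gap in the specification with a measurable consequence. If period means are analysed and the predictor is days since last dose, within-cycle dose information is lost. An effect confined to dosing days then appears at about one sixth to one quarter of its size, and at about one quarter to one half with 2 to 9 days of carry-over. If daily values are pooled, correlated days are treated as independent. These sizes rest on 5/28 dosing on schedule and the assumed carry-over lengths. The errors about the average and about chronotype variability need no such assumptions.

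Severity is low to moderate. The analysis is exploratory, and the primary feasibility endpoint is unaffected.

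**What to change.** In section 13.2.1:
- Define time since TMZ administration, and analyse it on daily values within patient, for example with patient as a random effect.
- Summarise each sleep variable separately for dosing and non-dosing days, as recorded in the diary, by arm. Keep pre-TMZ and post-treatment days apart.
- Keep period means for between-patient covariates and outcomes.
- Define chronotype variability as the SD of daily mid-sleep within each treatment cycle.
- Correct the sentence on stability and variability.
- Reconcile the 8-week collection period in 5.1 with the 2 months and typical 60 days in 7.2.

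No new data are needed. The cost is SAP wording and some programming, with more summary rows and fewer days behind each estimate.

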#### **4.4 Randomization**

Eligible patients will be randomized on a 1:1 basis to receive temozolomide at one of two time points: before 10:00 or after 20:00. A computer-generated randomization scheme is used to assign subjects. It is maintained centrally by the study statistician.

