## 9.0 STUDY CALENDAR

	Baseline	Beginning of each cycle of TMZ	1 month after the last TMZ treatment 	Follow-up 
Informed consent	X			
ActTrust Condor Instrument watch		Continuously beginning after the signing of consent but no more than 2 weeks prior to initiation of TMZ		
Sleep Questionnaire	X	X	X	
FACT-Br	X	X	X	
Randomization	X			
Tracking of hematologic toxicity 		X		
Review of medical record				X

1. Every 3 months by chart review looking for progression and survival.

2. From SOC blood draws.

3. To coincide with the patient's SOC end of treatment follow up visit with treating physician.

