## **13.0 STATISTICAL CONSIDERATIONS**

This study will include 40 patients with high grade glioma (WHO grades III or IV). Based on an extensive simulation regarding the sample size for translational and pilot studies, Piantadosi (2005) recommended that a sample size of 10 to 20 patients would provide a reasonable precision for estimating preliminary information. We therefore expect that the proposed sample size for this study will be adequate in estimating both safety and preliminary efficacy data.

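### Section 13.2.1 averages sleep measures over the collection period without a cut at the first temozolomide dose, and specifies no use of baseline sleep when relating them to dosing time

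*Combined protocol and SAP*

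**What the plan says.** Section 13.2.1 plans correlation and slope analyses of naps per day, nap duration, sleep duration, percent activity during waking, percent activity during sleep, chronotype and chronotype variability. The independent variables are tumor grade, time since temozolomide, time of day of temozolomide, time since diagnosis, tumor size and immune health. The summary rule is "Each variable will be calculated daily and averaged over the collection period". The section names no baseline sleep value, no change from baseline and no exclusion of days before the first dose.

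Baseline sleep is nevertheless collected. Section 7.2 states: "At baseline and at the beginning of each cycle of TMZ, the patient will complete a sleep questionnaire".

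The sections differ on when watch wear begins:

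- Section 5.1: "Patients will be given an ActTrust Condor Instrument watch after signing the consent form".
- Section 9.0: "Continuously beginning after the signing of consent but no more than 2 weeks prior to initiation of TMZ".
- Section 7.2: wear begins at the start of treatment or at enrolment, whichever comes later. A patient enrolled before treatment then has no pre-dose watch days.

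On the length of a period, section 5.1 states: "Actimetry data will be collected at corresponding time points with the return of the patient to clinic every 8 weeks". Section 7.2 describes a typical recording of 60 days per patient.

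**The concern.** Time of day of temozolomide is the randomized factor, so its relation to sleep is the one relation in this analysis that randomization protects. Two features weaken the estimate.

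First, if the watch is worn before the first dose, the first collection period mixes untreated with treated days. Untreated days cannot carry a dosing-time effect, so they pull the arm difference toward zero. The number of such days may also vary between patients.

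Second, with about 20 patients per arm, a chance difference in prior sleep habits passes straight into an unadjusted comparison. A baseline value for the same patient would remove part of that noise, and it is already being collected.

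The study is meant to supply pilot data for later chronotherapy trials, so a shrunken difference or an inflated SD would carry into their planning. The same document already uses baseline elsewhere: section 13.2.2.2 defines treatment-emergent laboratory abnormalities relative to baseline and counts them from the first dose. Sleep has no comparable rule.

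**Working it through.** **The plan's own figure.** Section 13.0 says "This study will include 40 patients with high grade glioma (WHO grades III or IV", and section 4.4 says "Eligible patients will be randomized on a 1:1 basis", so there are about 20 per arm. The size rests on a reference that "recommended that a sample size of 10 to 20 patients would provide a reasonable precision for estimating preliminary information". No effect size, SD, alpha or power is given for sleep, so there is no sleep calculation to reproduce.

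**Assumptions, not in the documents.** Two-sided 5%; SD of 1 for both pre-dose and on-treatment means; correlation ρ between them of 0.3 to 0.7; a constant dosing-time effect; a true difference set to give 80% power on post-dose days. By the normal approximation that difference is (1.960 + 0.842) × √(2/20) = 0.886 SD.

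**Step 1: share of untreated days.** With k pre-dose days in a period of T days, the expected arm difference is the true difference × (1 − k/T).

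| Pre-dose days k | Period T (days) | Shrinkage k/T |
|---|---|---|
| 0 (section 7.2; also allowed by 9.0) | 56 | 0% |
| 7 | 56 | 12.5% |
| 14 (upper limit in 9.0) | 56 | 25% |
| 14 | 60 | 23.3% |
| 14 (if the 8 weeks run from first dose) | 70 | 20% |

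Only the first period is affected. If periods are pooled, 14 days is 14/112 = 12.5% of two and 14/168 = 8.3% of three.

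**Step 2: effect on power.** Mixing also changes the between-patient SD. With w = k/T, the variance of the mixed mean is (1 − w)² + w² + 2w(1 − w)ρ. For k = 14, T = 56 and ρ = 0.5, this is 0.5625 + 0.0625 + 0.1875 = 0.8125, an SD of 0.901. The standardized effect is then 0.75/0.901 = 0.832 of its post-dose value.

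| ρ | Power, 7 pre-dose days | Power, 14 pre-dose days | Power, post-dose days only |
|---|---|---|---|
| 0.3 | 76% | 69% | 80% |
| 0.5 | 74% | 65% | 80% |
| 0.7 | 72% | 61% | 80% |

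**Step 3: gain from baseline adjustment.** For one covariate with N = 40, the variance factor is (1 − ρ²) × 37/36.

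| ρ | Variance factor | Power, post-dose days only |
|---|---|---|
| 0 | 1.03 | 78.9% |
| 0.3 | 0.94 | 82.6% |
| 0.5 | 0.77 | 89.1% |
| 0.7 | 0.52 | 97.2% |

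Break-even is where (1 − ρ²) × 37/36 = 1, so ρ = √(1/37) = 0.16.

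**Step 4: chance imbalance.** The standard error of a baseline arm difference is √(2/20) = 0.32 SD. A difference of at least 0.5 SD in either direction (0.5/0.316 = 1.58 standard errors) arises by chance about 11% of the time.

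**The case against.** *Pre-dose days may not be there at all.* A reader might infer from 5.1 and 9.0 that untreated days are certainly averaged in. The documents do not support that: 7.2 implies none, and the two weeks in 9.0 are a ceiling. This stands, and it is why the dilution is given as 0 to 25%.

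*They may drop out anyway.* Time since temozolomide has no value before the first dose, and data are analyzed as observed without imputation. That is plausible for day-level relations, but the plan does not say it, and it does not settle what enters a period average.

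*Baseline is used.* A reader might infer that baseline sleep data are never used. That is too strong: 7.2 assigns the questionnaire, together with the watch data, to assessing sleep/wake disruption. It gives no method, and 13.2.1 specifies no use of a baseline value.

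*Power is not the plan's yardstick.* Section 13.2.1 sets significance at R² of at least 0.8. For two equal arms R² = d²/(d² + 4), so the rule needs d = 4 SD, whereas 0.886 SD gives R² of about 0.16. Neither dilution nor adjustment would change a result under that rule. This lowers the stakes. It does not remove the defect, because 13.2.1 also calls for confidence intervals, and bias and precision still matter for those.

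*The aim is peripheral.* Endpoint 5 concerns sleep and treatment response; dosing time against sleep is part of a grid of 7 × 6 = 42 pairings in an exploratory analysis. Chance imbalance under randomization is imprecision, not bias. Both points stand and hold the priority down.

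**Conclusion.** The point holds in a limited form. Section 13.2.1 has no cut at the first dose and specifies no baseline sleep term. Sections 5.1, 7.2 and 9.0 disagree on whether pre-dose watch days exist. The resulting shrinkage is 0 to 25%, confined to the first collection period, and not expected to favor either arm. If 7.2 governs, there is no dilution, and only the unused baseline remains.

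The power figures illustrate size only. They rest on an assumed alpha, effect, correlation and equal SDs. A reader might multiply the effect by 0.75 with the SD held fixed and conclude that power falls to 56%. That is inconsistent with correlated pre- and post-dose sleep; the range for 14 days is 61% to 69%. Nor is the adjustment strictly free: it costs a degree of freedom and gains only if ρ exceeds about 0.16. The documents do not show that prior sleep dominates the comparison. The change is worth making because it costs little, with modest priority.

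**What to change.** In section 13.2.1, with matching edits to 5.1, 7.2 and 9.0:

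1. Reconcile the three watch-start statements and define the collection period, including the day it starts.
2. Summarize pre-dose days separately as baseline. Compute on-treatment means from the first dose onward, never across that date.
3. For the exploratory morning-versus-evening comparison, regress each on-treatment sleep variable on randomized arm with one baseline covariate, taken from the same source for all patients. Use the pre-dose watch mean if the reconciled design provides pre-dose wear. Otherwise use the matching item in the Quality of Sleep Questionnaire: mid-sleep and sleep duration from items 1 to 6, naps from item 10. Percent activity during waking, percent activity during sleep and chronotype variability have no matching item; leave them unadjusted if there are no pre-dose watch days.
4. Analyze the repeated insomnia items (item 12) with their baseline score as covariate.
5. Report estimates with 95% confidence intervals, labeled exploratory.

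The cost is protocol and SAP wording, some analysis code and one degree of freedom per model. No new visits, patients or instruments are needed. The main drawback is that a watch baseline of 0 to 14 days will be noisy or missing for some patients. As no imputation is planned, the number of patients in each adjusted model should be reported.
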